- n. Biopsy and tape strip samples to be collected pre dose. At Week 0, lesional and non lesional skin samples will be collected. At later timepoints, lesional skin samples will be collected.
- o. Participants who discontinue study intervention but do not terminate study participation are strongly encouraged to return for all protocol specified procedures for the safety follow up period and also for the ET Visit 5 weeks after last dose was administered. The procedures and evaluations listed for the ET visit should also be performed approximately 5 weeks after the last dose of study intervention. Participants who terminate study participation early should complete the procedures and evaluations listed for the ET visit approximately 5 weeks after their last administration of study intervention.
- p. Skin biopsy for all 10 participants of Part A and first 10 participants of Part B. At Week 0, lesional and non lesional skin samples will be collected. At Week 6, lesional skin samples will be collected.
- q. Skin biopsy for no participants in Part A, 20 last participants in Part B, and all participants in Part C. At Week 0, lesional and non lesional skin samples will be collected. At Week 16, lesional skin samples will be collected.

- r. Skin barrier function assessment should be evaluated together with tape stripping. Skin barrier function evaluation before tape stripping and after every 5 tapes.
- s. Vital signs (Heart rate, respiratory rate, temperature, blood pressure) to be collected every 30 mins between 0 to 4 hrs. This applies to the first 2 infusions only.
- t. For the first 2 doses, the study drug will be infused over approximately 2 hours to reduce the risk for IRR, followed by at least approximately a 2 hour observation. For the subsequent infusions, the infusion time may be decreased to approximately one hour with a minimum of approximately 1 hour observation period.
- u. Triplicate ECG to be done pre dose and post end of first infusion (after approximately 2 hours), at Week 0 only.
- v. Vital signs (heart rate, respiratory rate, temperature, blood pressure) to be collected approximately every 30 mins between 0 to 2 hours for infusions 3 through 15. This does not apply to the first 2 infusions.
- w. Additional serial TEWL, SCH, and EIS measurements will be acquired after every 5 tape strips at Weeks 0, 4, and 16.

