Data that may potentially unblind the intervention assignment (ie, study intervention serum concentrations, anti-JNJ-77474462 antibodies, study intervention preparation/accountability data, intervention allocation) will be handled with special care to ensure that the integrity of the blind is maintained and the potential for bias is minimized. This can include making special provisions, such as segregating the data in question from view by the investigators, clinical team, or others as appropriate until the time of DBL and unblinding.

Under normal circumstances, the blind should not be broken until all participants have completed the study and the database is finalized. Otherwise, the blind should be broken only if specific emergency intervention/course of action would be dictated by knowing the intervention status of the participant. In such cases, the investigator may in an emergency determine the identity of the intervention by contacting the IWRS. While the responsibility to break the intervention code in emergency situations resides solely with the investigator, it is recommended that the investigator contact the sponsor or its designee if possible to discuss the particular situation, before breaking the blind. Telephone contact with the sponsor or its designee will be available 24 hours per day, 7 days per week. In the event the blind is broken, the sponsor must be informed as soon as possible. The date and reason for the unblinding must be documented in the appropriate section of the eCRF and in the source document. The documentation received from the IWRS indicating the code break must be retained with the participant's source documents in a secure manner.

For the purpose of the interim analysis of safety data and preliminary PK, efficacy, and PD analysis, designated sponsor personnel will be unblinded to the relevant data as is required (Section 8.4, Pharmacokinetics and Immunogenicity). The randomization code will be disclosed to those authorized and only for those participants included in the interim analysis. All site personnel and participants will remain blinded to the treatment assignments until the last participant completes the Week 20 evaluations and the final database is locked.

Participants who have had their intervention assignment unblinded should continue to return for scheduled evaluations and are not eligible to receive further study intervention.

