 - A participant has symptoms suggestive of active TB based on follow-up assessment questions and/or physical examination or has had recent close contact with a person with active TB and cannot or will not undergo additional evaluation.
 - A participant undergoing evaluation has a chest radiograph with evidence of current active TB and/or a positive QuantiFERON-TB test result and/or 2 indeterminate QuantiFERON-TB test results on repeat testing (refer to [Section 8.2.9](#), Tuberculosis Evaluations) (and/or a positive tuberculin skin test result in countries in which the QuantiFERON-TB test is not approved/registered or the tuberculin skin test is mandated by local health authorities).

- A participant receiving treatment for latent TB discontinues this treatment prematurely or is noncompliant with the therapy.
- The participant is unable to adhere to the study visit schedule or comply with protocol requirements.
- Abnormal liver tests as outlined in Section 10.7, Appendix 7: Liver Safety: Suggested Actions and Follow-Up Assessments.
- Use of prohibited corticosteroids:
 - IM and IV formulations
 - Oral corticosteroids for more than 10 days.
- The participant has his/her treatment assignment unblinded by the investigator.
- Sponsor decision.

If a participant discontinues study intervention for any reason before the end of the double-blind phase, then the end-of-intervention assessments should be obtained and scheduled assessments off study intervention should be continued. Study intervention assigned to the participant who discontinued study intervention may not be assigned to another participant. Additional participants will not be entered.

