Participants who decide to discontinue study intervention administration for reasons other than those outlined above must be interviewed by the investigator to determine if a specific reason for discontinuing study intervention can be identified. Participants should be explicitly asked about the possible contribution of AEs to their decision to discontinue study intervention; investigators should confirm that any AE information elicited has been documented. If a participant elects to discontinue study intervention due to an AE, the event should be recorded as the reason for study intervention discontinuation, even if the investigator's assessment is that the AE would not require study intervention discontinuation. The reason for study intervention discontinuation must be documented in the eCRF and in source documents. Study intervention assigned to a participant who discontinues may not be assigned to another participant.

A participant will not be automatically withdrawn from the study if he or she must discontinue treatment before the end of the treatment regimen. Participants who discontinue study intervention but do not terminate study participation are strongly encouraged to return for all protocol-specified procedures and evaluations for approximately 5 weeks following the last dose of study intervention. The procedures and evaluations listed for the early termination visit should also be performed approximately 5 weeks after the last dose of study intervention.

All procedures and evaluations must be conducted prior to a participant's withdrawal of consent.

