Participants who experience close contact with an individual with active TB during the conduct of the study must have a repeat chest radiograph, a repeat QuantiFERON-TB (or T-SPOT for sites in Japan) test, a repeat tuberculin skin test in countries in which the QuantiFERON-TB test is not approved/registered or the tuberculin skin test is mandated by local health authorities, and, if possible, referral to a physician specializing in TB to determine the participant’s risk of developing active TB and whether treatment is warranted. Study intervention administration should be interrupted during the investigation. A positive QuantiFERON-TB (or T-SPOT for sites in Japan) test or tuberculin skin test result should be considered detection of latent TB. Participants with a newly identified positive QuantiFERON-TB (or T-SPOT for sites in Japan or tuberculin skin) test result must undergo an evaluation to rule out active TB and initiate appropriate treatment for latent TB. Appropriate treatment for latent TB is defined according to local country guidelines for immunocompromised participants. If no local country guidelines for immunocompromised participants exist, US guidelines should be followed, or the participant will be excluded from the study. If the QuantiFERON-TB test result is indeterminate, the test should be repeated. For sites in Japan, a participant whose first T-SPOT test result is borderline should have the test repeated. Participants should be encouraged to return for all subsequent scheduled study visits according to the protocol. Participants who discontinue treatment for latent TB prematurely or who are noncompliant with therapy must immediately discontinue further administration of study

intervention and be encouraged to return for all subsequent scheduled study visits according to the SoA (Section 1.3).

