8.4. Pharmacokinetics and Immunogenicity

Venous blood samples will be collected for the measurement of serum bermekimab concentrations and detection of antibodies to bermekimab at the time points presented in the SoA (Section 1.3).

At visits in which serum bermekimab concentration and/or antibodies to bermekimab will be evaluated, 1 venous blood sample of sufficient volume should be collected, and each serum sample should be divided into 3 aliquots: 1 for serum concentration of bermekimab, 1 for antibodies to bermekimab, and 1 back-up.

Serum samples will also be collected at the final visit from participants who terminate study participation/intervention early. Blood samples collected for serum bermekimab concentrations and/or antibodies to bermekimab may also be used for exploratory biomarker analyses.

A random venous blood sample for population PK analysis will be collected from the first 20 participants of the study on any day between Weeks 2 to 12, except on the days of the scheduled study visits. If possible, we would like to encourage obtaining this sample between Week 2 and Week 6, although if it is done after Week 6, it would not constitute a protocol deviation. Additionally, this blood sample must be collected at least 24 hours prior to or after the actual time

of study intervention administration. All the remaining participants (last 20 participants of Part B, and all 20 participants of Part C) may choose to also participate in the collection of this population PK sample as optional. Each population PK serum sample will be divided into 2 aliquots: 1 for serum concentration of bermekimab and a back-up.

The exact dates and times of blood sample collection must be recorded in the laboratory requisition form. See the laboratory manual for further information regarding collection, handling, and shipment of biological samples. Genetic analyses will not be performed on these serum samples. Participant confidentiality will be maintained.

Pharmacokinetic Analytical Procedures

Serum samples will be analyzed to determine serum bermekimab concentrations using a validated, specific, and sensitive immunoassay method by or under the supervision of the sponsor. The sponsor, or its designee, under conditions in which the participants' identity remains blinded, will assay these samples.

Immunogenicity Analytical Procedures

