9.4.2. Primary Endpoint

The primary efficacy endpoint is the proportion of participants with EASI-75 at Week 16.

Primary Estimand: The primary estimand (ie, a precise definition of the primary targeted treatment effect) is defined by the following 5 attributes:

- **Population:** adult participants with moderate-to-severe AD
- **Variable/endpoint:** Binary response variable, where a responder is defined as a participant achieving an EASI-75 response at Week 16. A participant with an intercurrent event (ICE) in categories 1 to 3 defined below will be considered a non-responder.
- **Study intervention:**

Bermekimab 800 mg, 1200 mg, dose C mg IV qw

Placebo IV qw

- **Intercurrent Events:**

Table 4: Analysis Strategy for Addressing Intercurrent Events (ICEs)	
Intercurrent Events (ICEs)	Analysis Strategy for Addressing Intercurrent Events (ICEs)
1. Discontinuation of study intervention due to lack of efficacy, an AE of worsening of AD prior to Week 16 2. Initiation of a protocol-prohibited medication or therapy during the study that could improve AD prior to Week 16 3. Initiation of rescue medication for AD prior to Week 16	Composite Strategy: Participants with these intercurrent event are considered as EASI-75 non-responders after these events. The occurrence of these intercurrent event being captured in the variable definition.
4. Discontinuation of study intervention for reasons other than above defined reasons prior to Week 16	Treatment policy: Use observed data regardless of whether or not this intercurrent event had occurred

- **Population level summary:** Difference in the proportions of participants achieving an EASI-75 response at Week 16 between the bermekimab and placebo treatment groups.

Primary Endpoint Analysis

In the primary efficacy analysis, data from all randomized participants who received at least 1 administration of study intervention will be analyzed according to their assigned treatment group. The primary endpoint will be analyzed at Week 16 based on the primary estimand and the number and proportion of participants who achieve an EASI-75 response at Week 16 will be summarized for each treatment group. To address the primary objective, a Fisher's exact test at an alpha level of 0.1 will be used to compare each bermekimab group separately with placebo. The proportion difference between each bermekimab group and placebo group and its 2-sided 90% CI will be provided.

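### Protocol 7.1 and the SoA give unreconciled follow-up rules after treatment stops, so Week 16 EASI may go uncollected for early stoppers whom 9.4.2 means to analyse on observed data

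*Protocol*

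**What the plan says.** **Rule that follow-up continues.** Protocol 7.1, in the paragraph directly after the list of discontinuation reasons, covers a stop for any reason during the double-blind phase and says that "scheduled assessments off study intervention should be continued". It sets no end point. Two other sections agree for particular groups. Section 6.3: "Participants who have had their intervention assignment unblinded should continue to return for scheduled evaluations". Section 8.2.9.2, on participants who abandon or do not comply with latent-TB treatment: they must stop dosing "and be encouraged to return for all subsequent scheduled study visits according to the" SoA.

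**Rule with a 5-week span.** Later in the same Section 7.1, participants who stop treatment without leaving the study "are strongly encouraged to return for all protocol-specified procedures and evaluations for approximately 5 weeks following the last dose of study intervention", with the early termination (ET) procedures at about the same time. SoA footnote o encourages these same participants to "return for all protocol specified procedures for the safety follow up period and also for the ET Visit 5 weeks after last dose". It does not name the remaining treatment-period visits or Week 16. The footnote then gives people who leave the study the same visit: "Participants who terminate study participation early should complete the procedures and evaluations listed for the ET visit approximately 5 weeks after their last administration".

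**What the analysis needs.** Section 9.4.2 defines the primary endpoint as EASI-75 at Week 16. For ICE 4 (stopping for reasons other than lack of efficacy or an AE of worsening AD), Table 4 says: "Treatment policy: Use observed data regardless of whether or not this intercurrent event had occurred". The analysis text repeats that data observed after ICE 4 are used, and counts anyone without a usable Week 16 EASI as a non-responder.

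**The concern.** A treatment-policy strategy works only if the outcome is still measured after treatment stops. The protocol gives sites one instruction that secures this and two that can be read as ending at about 5 weeks. Footnote o is attached to the schedule that sites work from, and it gives those who stop treatment and those who leave the study the same 5-week visit. A site could reasonably take that visit as the last one.

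For an early stopper at such a site there would be no Week 16 EASI. The missing-data rule would then decide the outcome, and ICE 4 would in effect be handled by a composite (non-response) strategy, as ICEs 1 to 3 are. Sites could also differ in which instruction they follow. An EASI taken at the ET visit would not fill the gap: no text assigns it to Week 16, and SAP 5.1.1 uses nominal visits.

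**Working it through.** **Inputs.**
- Weekly dosing, Weeks 0 to 15 (Protocol 6.1, Table 2).
- Visits and doses within ±3 days of schedule, counted from the first dose (SoA footnote x).
- Follow-up of about 5 weeks, taken as 35 days (Protocol 7.1, SoA footnote o).
- Planned group sizes: 24 (1200 mg), 16 (dose C) and 12 (pooled placebo) (Protocol 9.2).

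**The plan's own 5-week figure.** For a participant who completes dosing, the last dose is at Week 15: 7 × 15 + 35 = 140 days = Week 20, the final visit. The 5-week interval therefore matches the end of the regular schedule.

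**Timing for early stoppers.** Count days from the first dose (day 0). Week 16 is day 7 × 16 = 112, with a window of 109 to 115. For a last dose at Week L, the 5-week point is day 7L + 35 if dosed on schedule and day 7L + 38 if dosed 3 days late.

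| Last dose | On schedule (7L + 35) | 3 days late (7L + 38) | Against window opening, day 109 |
|---|---|---|---|
| Week 0 | 35 | 38 | far short |
| Week 5 | 70 | 73 | far short |
| Week 9 | 98 | 101 | 8 to 11 days short |
| Week 10 | 105 | 108 | 1 to 4 days short |
| Week 11 | 112 | 115 | inside the window |
| Week 12 | 119 | 122 | span covers Week 16 |

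Last doses at Weeks 0 to 9 clearly miss the window. Week 10 is borderline, because an approximate 5 weeks could stretch to reach it. From Week 11 on, the 5-week span of 7.1 reaches or covers Week 16.

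**The two readings side by side.**
- If scheduled assessments continue, every ICE 4 participant who remains and returns has a Week 16 EASI. The affected set is empty.
- If the 5-week text is taken as the limit, ICE 4 participants with a last dose at Weeks 0 to 9 have none, and 9.4.2 scores them as non-responders.

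**Effect per participant.** Only a stopper who would have been a Week 16 responder is misclassified. One such person lowers the group's rate by 1/24 = 4.2 points (1200 mg), 1/16 = 6.3 points (dose C) or 1/12 = 8.3 points (placebo). In a bermekimab group this shrinks the difference from placebo; in the placebo group it enlarges it. A stopper who would not have responded changes nothing.

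**The case against.** The strongest reply is that the protocol already intends Week 16 collection. The opening instruction in 7.1 covers every reason for stopping, and 6.3 and 8.2.9.2 agree with it. Section 7.1 says that stopping treatment does not mean automatic withdrawal, and 7.2 limits study withdrawal to loss to follow-up, withdrawn consent and death. Both 5-week texts use the word also for the ET visit, which fits a post-dose safety visit added to the schedule. Most of this stands: continued visits are the better reading, and no text cancels Week 16. But neither 5-week text says that it is an addition to the remaining visits. The phrase about returning for a period of some 5 weeks sits badly beside an open-ended instruction in the same section.

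The affected set is also narrow: ICE 4 only, last dose by Week 9 or 10, still in the study and willing to return, at a site that takes 5 weeks as the end. Return is encouraged, not compelled, on either reading. Section 9.4.2 has a rule for missing values and promises additional analyses with other data handling. All of this limits the weight of the point. None of it reconciles the texts.

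A reader might infer that the protocol ends follow-up at 5 weeks, so that early stoppers are bound to lack Week 16 data. The documents do not support that, given the sections that continue visits.

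**Conclusion.** The inconsistency is real and should be corrected. Followed literally, the later text of 7.1 or footnote o leaves ICE 4 participants with a last dose at Weeks 0 to 9 (Week 10 borderline) without a Week 16 EASI, and moves them from observed data to imputed non-response. This rests on 5 weeks meaning 35 days, the ±3-day window, and a site treating the 5-week visit as the last.

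The size is not established. The documents give no discontinuation rate and no split of stops by reason or timing. A reader might infer a loss of power or a bias against bermekimab; neither follows, because the sign depends on which group the misclassified responders are in.

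Nor does the point undermine a final hypothesis test. After early termination, SAP 5.3.2 and Appendix 2 plan listings and no formal analysis. What remains at stake is the protocol's planned primary analysis and which Week 16 values exist to be listed.

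**What to change.** Reconcile the later text of Protocol 7.1 and SoA footnote o with the opening instruction in 7.1. Suggested wording: participants who discontinue study intervention but remain in the study should complete the scheduled efficacy assessments, including EASI, through Week 16, in addition to the visit approximately 5 weeks after the last dose. Footnote o should also separate these participants clearly from those who leave the study, for whom the ET visit can be the last.

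The cost is a wording change and a few visits for early stoppers that are already in the schedule. Those who decline to return would still be missing at Week 16 and would still fall under the non-responder rule.

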7.1.1. Liver Chemistry Stopping Criteria

Discontinuation of study intervention for abnormal liver tests is required by the investigator when a participant meets one of the conditions outlined in Section 10.7, Appendix 7: Liver Safety: Suggested Actions and Follow-Up Assessments or in the presence of abnormal liver chemistries not meeting protocol-specified stopping rules if the investigator believes that it is in best interest of the participant.

7.2. Participant Discontinuation/Withdrawal From the Study

A participant will be withdrawn from the study for any of the following reasons:

- Lost to follow-up
- Withdrawal of consent
- Death.

When a participant withdraws before study completion, the reason for withdrawal is to be documented in the eCRF and in the source document. If the reason for withdrawal from the study is withdrawal of consent then no additional assessments are allowed.

Withdrawal of Consent

Withdrawal of consent should be a very unusual occurrence in a clinical trial; the investigator should make every effort to maintain good participant relationships to avoid withdrawals of consent. For participants who truly request withdrawal of consent, it is recommended that the participant withdraw consent in writing; if the participant or the participant's representative refuses to do so or is physically unavailable, the study-site should document the reason for the participant's failure to withdraw consent in writing, sign the documentation, and maintain it with the participant's source records. When a participant withdraws before completing the study, the reason for withdrawal is to be documented in the eCRF and in the source document. Study intervention assigned to the withdrawn participant may not be assigned to another participant. Participants who withdraw will not be replaced.

